16. ANNEX 3: RECOMMENDED STUDY CONTACT SCHEDULE

Table 4: Expected Contacts With Participants and HCPs

Expected Contacts ¹ with Participant	Expected Contacts ¹ with Participant's HCP (e.g., Obstetrician)	Expected Contacts ¹ With Pediatric HCP (e.g., Pediatrician) ²
Enrollment	Enrollment	1, 2, 6, 12, 18, and 24 months of age ⁵ : for
First trimester ³ : for pregnancy status follow-up Second trimester ³ : for pregnancy status follow-up	6 to 7 months of gestation: for Prenatal Follow-Up 4 weeks after EDD ⁴ : for Pregnancy Outcome Follow-Up	Pediatric Follow-Up
Third trimester ³ : for pregnancy status follow-up		

Contacts for this study are not mandated, but registries will inform participants and HCPs of the expected contact schedule and make every effort to ensure data are entered for each expected contact.

² Live births only.

³ Follow up with the HCP, if needed.

⁴ Follow up with other practitioners or the participant, if needed.

⁵ Follow up with the participant, if needed.

Table 5: Recommended Study Contact Schedule

	Enrollment	Prenatal	Prenatal Follow-Up		Pediatric Follow-Up
Data Collection	Initial Report/Registration by Participant and/or HCP ¹	Contact Participant or HCP at Each Trimester	Contact HCP at Approximately 6 to 7 Months of Gestation	Contact HCP(s) at Approximately 4 Weeks After EDD ²	Contact Pediatric HCP at Approximately 1, 2, 6, 12, 18, and 24 Months of Age ³
Informed Consent ⁴	X				
Participant Demographics	X				
Participant Contact Information and Secondary Contact Information	Х	X	Х		
Medical History	X		X		
Pregnancy History and Current Pregnancy Information ⁵	X				
Pregnancy Outcome Risk Factors ⁶	X	X	X	X	
Prenatal Testing	X		X		
Current Pregnancy Status	X	X	X		
Gestational Age (in Weeks)		X	X	X	
Weight Gain During Pregnancy		X	X	X	
Nusinersen Exposure History and Adherence	X	X	X	X	

Data Collection	Enrollment Initial Report/Registration by Participant and/or HCP ¹	Prenatal Follow-Up		Pregnancy Outcome Follow-Up	Pediatric Follow-Up
		Contact Participant or HCP at Each Trimester	Contact HCP at Approximately 6 to 7 Months of Gestation	Contact HCP(s) at Approximately 4 Weeks After EDD ²	Contact Pediatric HCP at Approximately 1, 2, 6, 12, 18, and 24 Months of Age ³
Prior and Current Medications Other Than Nusinersen	X ⁷	X	X	X	
Possible SMA Symptoms ⁸			X	X	
Pregnancy Outcome				X	
Type of Delivery				X ⁹	
Complications During Pregnancy and/or Birth with Associated Notable Dates		X	X	X	
Neonatal or Pediatric Illness ¹⁰				X	X
Infant Characteristics				X ¹¹	X ¹²
Neurobehavioral Impairment					X ¹³
Evidence of Any Abnormality Not Identified at Birth (if Applicable)					X
Pregnancy-related and Pregnancy Outcome Serious Adverse Events					

If the reporter is the participant, additional contact will be made with the participant's HCP to obtain medical information.

- ² If a participant experiences an adverse pregnancy outcome or has a pregnancy termination or an abortion of unknown cause, the HCP is encouraged to report this outcome as soon as possible.
- ³ The registry will contact the pediatric HCP, designated either at enrollment or during one of the previous collection periods.
- ⁴ Informed consent (written or verbal per local regulations or ethics committee requirements) must be obtained for the pregnancy study (if not already adequately covered by the existing registry consent). If the participant is a minor, written consent must be obtained from the parent or legal guardian. A release of medical information will also be obtained from the parent or the infant's Personal Representative so that the registry can contact the pediatric HCP for the 1, 2, 6, 12, 18, and 24 month follow-up visits.
- ⁵ Details on previous pregnancies (if applicable) may include complications, outcomes, MCMs or developmental abnormalities, birth length, and birth weight. Current pregnancy information may include date of LMP, EDD, method of pregnancy confirmation, health assessments, prenatal testing, and outcome (if reported retrospectively).
- ⁶ Risk factors include smoking, use of caffeine (> 200 mg per day), use of alcohol, and use of recreational drugs.
- ⁷ Current medications and past medications up to 6 months prior to the first day of the participant's LMP before conception.
- ⁸ As determined by the HCP (e.g., muscle weakness, change in gait, tremor, respiratory changes).
- ⁹ For example, vaginal or cesarean delivery (C-section). Report should include whether labor/delivery was induced early and, if applicable, the reason for induction.
- ¹⁰Neonatal or pediatric illnesses (e.g., prematurity, respiratory dysfunction, birth trauma) that resulted in hospitalization, including any treatments (e.g., drug therapies).
- ¹¹Gestational age at birth (in weeks), sex, weight, length, head circumference, birth order (for multiple births), Apgar scores, breastfeeding status, genetic diagnoses (including SMA) if applicable, medications, and any MCM noted, including description and attribution.
- ¹²Feeding behavior, head circumference, weight, length, developmental milestones, breastfeeding status, genetic diagnoses (including SMA) if applicable, and medications.
- ¹³Neurobehavioral impairment will be measured starting at 2 months of age.

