8.2.1. Pregnancy and Infant Outcomes

Pregnancy outcomes include pregnancy loss (pregnancy termination, spontaneous abortion, and fetal death [stillbirth]) and live birth (premature birth and full-term birth). Within each of these categories, the fetus or infant will be evaluated as to the presence or absence of anomalies or other fetal effects.

Pregnancy Loss

- Pregnancy termination (any induced or voluntary fetal loss during pregnancy)
- Spontaneous abortion (< 20 weeks of gestation)
- Fetal death, including stillbirth (fetuses born dead at ≥ 20 weeks of gestation or fetuses born dead at ≥ 350 g if gestational age is unknown), which is further classified as follows:
 - Early fetal loss (fetal death occurring at ≥ 20 weeks but ≤ 28 weeks of gestation)
 - Late fetal loss (occurring at \geq 28 weeks of gestation)

Live Birth

• Premature birth (delivered < 37 weeks)

CONFIDENTIAL

• Full term birth (delivered \geq 37 weeks)

Infant deaths up to 52 weeks of age, as defined in Section 9.3, will be reported among live births.

Major Congenital Malformations

- Interchangeably referred to as congenital malformations, congenital anomalies, and birth defects.
- Abnormalities in structural development that are medically or cosmetically significant, are present at birth, and persist in postnatal life unless or until repaired, as evaluated by independent advisors.

In addition, SGA births, abnormal postnatal growth and development (i.e., social/emotional, language/communication, neurocognitive, movement/physical development milestones) up to 2 years of age, ectopic pregnancies, and molar pregnancies will be reported for each pregnancy outcome (see Section 9.3). Given that SMA is a genetic condition, it is possible that babies born to an individual with SMA will also have SMA. Therefore, the diagnosis of SMA in infants will also be collected.

Maternal death during pregnancy, labor, delivery, or up to 12 weeks after delivery will be reported. Infant deaths occurring up to 52 weeks of age will also be reported.

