9.2.1. Study Contact Schedule

There are no mandated physician visits for this study. Instead, it is expected that participants and HCPs will be contacted according to the recommended study contact schedule (Section 16). While contacts for this study are not mandated, registries will inform participants and HCPs of the expected contact schedule and make every effort to ensure data are entered for each expected contact. The registries will also utilize

CONFIDENTIAL

electronic medical record review to collect data when contacting participants/HCPs is not feasible.

Pregnancy information will be collected by the registries from HCPs to determine eligibility. The registries will obtain informed consent for the pregnancy study (if not already adequately covered by the existing registry consent) prior to collecting data from the participant for the study.

After the participant enrolled in the registry provides consent for the pregnancy study, current demographic data, contact information, and pregnancy information, in addition to relevant medical history at the time the pregnancy is reported, will be collected. The contact information will be confidential and remain on site. Thereafter, it is expected that the participant will be contacted once per trimester to update contact information and ascertain the occurrence of a pregnancy outcome. It is expected that the participant's obstetric HCP will be contacted at 6 to 7 months of gestation for the Prenatal Follow-Up and at approximately 4 weeks after the EDD for the Pregnancy Outcome Follow-Up. At approximately 1, 2, 6, 12, 18, and 24 months after birth, it is expected that the pediatric HCP (or the participant) will be contacted for a Pediatric Follow-Up. All data collected will be entered into the registry. See Table 4 for a description of the expected contacts with participants and HCPs.

If the participant experiences an adverse pregnancy outcome or has a pregnancy termination or an abortion of unknown cause, the HCP is encouraged to report this outcome as soon as possible rather than to wait until the scheduled follow-up contact.

See Section 9.3.2 and Table 5 for the recommended information to be collected at different periods.

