9.3.1.12. Abnormal Postnatal Growth and Development

Domains of developmental milestones (i.e., social/emotional, language/communication, neurocognitive, movement/physical development milestones) by age up to 52 weeks will be defined by guidelines provided by the CDC [CDC 2020]. As recommended by the

CONFIDENTIAL

CDC, the World Health Organization Growth Charts (suitable for use in the US from birth to 24 months) will be applied for this study, where infant growth measurements will be used to estimate gender-specific weight-for-length, head circumference-for-age, length-for-age, and weight-for-age percentiles.

Postnatal growth deficiency or FTT will be defined as weight in the < 10th percentile for sex and chronological age using international growth reference standards from WHO for children aged 0 to 24 months. Postnatal growth deficiency will be evaluated at 1, 2, 6, 12, 18, and 24 months of age.

Infant developmental deficiency will be defined as failure to achieve developmental milestones for chronological age defined by CDC. Infant developmental deficiency will be evaluated at 1, 2, 6, 12, 18, and 24 months of age.

Developmental milestones will be collected as part of routine clinical practice with pediatrician-determined results of infant status (i.e., below, above, or at age-appropriate achievement) in each of the domains listed above. "Ages and Stages" or similar standardized assessments may be collected for this study if performed as part of routine clinical care. No additional information will be mandated for collection as part of this study.

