9.7. Data Analysis

9.7.1. General Discussion of the Analysis

All participants will be reviewed based on earliest exposure within the relevant nusinersen exposure window.

The registries and Biogen Epidemiology and Global Safety will carefully review each pregnancy outcome and the frequency of adverse pregnancy outcomes. For this study, gestational weeks are calculated beginning from the first day of the participant's LMP. If the date of LMP is not available, the EDD may be used. If the gestational week is

inconsistent with the exposure dates and/or the dates of outcomes (outside of 1 week for the first trimester, outside of 2 weeks for the second and third trimesters) and a corrected EDD (i.e., generally by ultrasound) is available, the corrected EDD is used for gestational week calculations.

Descriptive analyses will be performed to analyze the risks of MCMs, spontaneous abortions, SGA births, and abnormal postnatal growth and development.

Statistical analyses may be performed to examine potential increases in risks of MCMs, spontaneous abortions, SGA births, and abnormal postnatal growth and development as compared with the expected background prevalence. The prevalence and 95% CIs for study participants may be calculated to assess the presence of any excessive risk associated with nusinersen exposure.

All analyses will be conducted on an overall basis as well as grouped by the earliest trimester of exposure. For MCMs, analyses will be conducted only for participants who have exposure in the first trimester. In the absence of treatment initiation during the second and third trimester of pregnancy, the subgroups with small sample sizes may be collapsed as needed. Other adverse pregnancy outcomes will be examined similarly as the sample size permits.

A periodic review of the study will be performed by monitoring reports of adverse pregnancy outcomes for nusinersen (see Section 9.7.4).

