9.7.3. Methods of Analysis

Each pregnancy outcome will be classified into the categories described in Section 9.3 and will be collected and reported separately. Data will be presented in aggregate tables in the interim and final reports.

All analyses will be conducted on an overall basis, as well as stratified by earliest trimester of exposure. For MCMs, analyses will be conducted only for participants who have exposure in the first trimester. The prevalence and 95% CIs of spontaneous abortions, MCMs, SGA births, and abnormal postnatal growth and development will be CONFIDENTIAL

The information contained herein may not be used, disclosed, or published without the written consent of Biogen MA Inc.

calculated. Other negative pregnancy outcomes will be similarly examined as the sample size permits. Infants with minor malformations, chromosomal abnormalities, genetic syndromes, positional defects, and prematurity-related defects will be excluded from the primary analyses related to MCM prevalence; these outcomes will be reported in the interim and final reports. Details of the analysis will be provided in the statistical analysis plan.

If sufficient enrollment numbers are obtained, analyses will also be stratified according to maternal age, gestational age at enrollment, medical condition at time of pregnancy that may affect pregnancy outcome (including but not limited to respiratory, neuropsychiatric, metabolic, cardiovascular, infectious, hematological disease or impairment), and other important risk factors (e.g., concurrent medications and substance use).

Demographic information, clinical characteristics, and other potential factors that may affect pregnancy outcome will be described.

The actual date of delivery (not the EDD) will be used in all analyses. EDD will only be used to schedule outreach to HCPs to ascertain the outcome of an expected birth.

For each interim analysis, pregnancy and infant outcomes will be analyzed cumulatively from the beginning of the study.

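### The outcome contact is dated from the EDD but pediatric contacts from birth, so for early births the 1-month contact, and sometimes the 2-month contact, falls due first

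*Protocol*

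**What the plan says.** The protocol's contact schedule uses two starting points.

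- **Outcome contact.** Table 5 heads the Pregnancy Outcome Follow-Up column "Contact HCP(s) at Approximately 4 Weeks After EDD", and Sections 9.2.1 and 9.3.2.4 give the same timing. Section 9.7.3 explains the role of this date: "EDD will only be used to schedule outreach to HCPs to ascertain the outcome of an expected birth". The Pregnancy Outcome row of Table 5 is marked in this column only.
- **Pediatric contacts.** Table 5 has "Contact Pediatric HCP at Approximately 1, 2, 6, 12, 18, and 24 Months of Age". Section 9.2.1 ties them to delivery: "At approximately 1, 2, 6, 12, 18, and 24 months after birth".

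The early pediatric contacts feed stated outcomes. Section 9.3.1.12 says "Postnatal growth deficiency will be evaluated at 1, 2, 6, 12, 18, and 24 months of age", with developmental deficiency at the same ages, and Section 9.3.1.13 starts neurobehavioral assessment at 2 months. Section 9.7.3.1.4 divides the number of growth and development events by all live births.

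There are other ways to hear of a birth. Participants are contacted once per trimester, and an outcome assessment must follow if an outcome has occurred (Sections 9.2.1 and 9.3.2.2). After an adverse outcome, a termination or an abortion of unknown cause, "the HCP is encouraged to report this outcome as soon as possible" (Table 5, footnote 2). The registry also contacts the HCP earlier if the participant reports an adverse outcome or a termination (Section 9.3.2.4). Electronic records are a further source.

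**The concern.** A registry working to this schedule has one fixed date on which it finds out how a pregnancy ended, and that date does not move when the infant arrives early. The pediatric dates do move. The earlier the birth, the further the first pediatric contacts fall ahead of the contact that would tell the registry there is an infant to follow.

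Timeliness and completeness of the 1- and 2-month data then depend on gestational age at birth, and premature birth is itself a listed outcome (Section 8.2.1). Growth deficiency is defined by weight for chronological age, so preterm infants are plausibly the likeliest to meet it early, and their early contacts are the ones that come due unseen. If some of these assessments are never retrieved, a denominator of all live births turns the gap into a count of no event.

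**Working it through.** The protocol states no figure on this point, so there is none to reproduce. The check is date arithmetic.

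**Inputs**
- Origin of gestational age: "gestational weeks are calculated beginning from the first day of the participant's LMP" (Section 9.7.1).
- EDD: day 280 from LMP (40w0d). This is an assumption; the protocol does not state it.
- Outcome contact: EDD + 28 days = 280 + 28 = day 308 (44w0d).
- Pediatric contact at m months: gestational age at birth + m × 30.44 days. As a sensitivity check, 28-day months.

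**Thresholds.** A pediatric contact falls due first when gestational age at birth is below 308 − m × 30.44 days.
- 1 month: 308 − 30.4 = 277.6 days = 39w4d (40w0d with 28-day months).
- 2 months: 308 − 60.9 = 247.1 days = 35w2d (36w0d with 28-day months).
- 6 months: 308 − 182.6 = 125.4 days = 17w6d (20w0d with 28-day months). This and the later contacts are not affected in practice.

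**Size of the lead.** Infant's age at the outcome contact = 308 − gestational age at birth; lead = that age − m × 30.44. A negative value means the pediatric contact comes after the outcome contact.

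| Birth at | Age at outcome contact (days) | 1-month lead (days) | 2-month lead (days) |
|---|---|---|---|
| 41w | 21 | −9.4 | −39.9 |
| 40w | 28 | −2.4 | −32.9 |
| 39w | 35 | 4.6 | −25.9 |
| 38w | 42 | 11.6 | −18.9 |
| 37w | 49 | 18.6 | −11.9 |
| 36w | 56 | 25.6 | −4.9 |
| 35w | 63 | 32.6 | 2.1 |
| 34w | 70 | 39.6 | 9.1 |
| 32w | 84 | 53.6 | 23.1 |
| 28w | 112 | 81.6 | 51.1 |

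**Can the third-trimester contact fill the gap?** Take a birth at 32w0d (day 224). The 1-month contact is due on day 224 + 30.4 = 254.4 (36w2d) and the 2-month contact on day 224 + 60.9 = 284.9 (about 40w5d). A trimester contact made after the birth and before those dates reveals it in time. One made before the birth does not, and the protocol fixes no week for it.

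**Denominator.** With N live births and u infants not assessed at a given age, the stated formula gives the proportion among assessed infants multiplied by (N − u)/N. Section 9.5 expects 20 pregnancies. Applying the 15% to 20% miscarriage background in Section 7.1.2 gives 20 × 0.85 = 17 to 20 × 0.80 = 16 live births. This is an assumption that ignores other losses and loss to follow-up. With N = 16, one unassessed infant gives a factor of 15/16 = 0.94 and two give 14/16 = 0.875.

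**The case against.** The strongest reply is that a contact retrieves data and is not itself an examination. The protocol mandates no visits. Milestones and neurobehavioral status come from routine pediatric care (Sections 9.3.1.12 and 9.3.1.13), so a late call will often find a dated record already there, and each pediatric contact also asks about abnormalities since the last one. This stands: the usual result is late data, not lost data. It does not make retrieval certain, and the protocol has no instruction to recover the earlier ages when a birth is learned late.

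A reader might infer several stronger conclusions that the documents do not support.

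- *That the 1-month contact always comes first.* It does not for births on or after the EDD, and at 39 weeks the gap of about 5 days lies within the approximate timing. Any percentage of births affected would need an assumed gestational-age distribution and would count these trivial cases.
- *That live births have no early route.* Section 9.3.1.3 treats birth weight under 2500 g as an adverse pregnancy outcome, so such births can come under the early-reporting wording. Electronic records are listed as a source at each trimester and at the outcome follow-up (Sections 9.3.2.2 and 9.3.2.4), and more generally in Section 9.4. The pediatric HCP may be named as early as enrollment (Table 5, footnote 3). Even so, HCP reporting is only encouraged, knowing whom to call does not tell the registry that a birth has happened, and nothing in the wording clearly covers an otherwise uncomplicated early live birth.
- *That early deaths go unseen.* An infant born at 32 weeks is 84 days (12 weeks) old at the outcome contact, but the 1- and 2-month contacts lie inside that period. Deaths are classified by age at death (Sections 9.3.1.9 to 9.3.1.11), so one learned of later is still counted correctly.
- *That the early estimates are certainly biased toward normal.* That needs assessments that are never recovered, and the protocol states no rule for unassessed infants. The analysis plan, which is not at hand, may set one. What remains is the formula the protocol does state, which takes all live births as the denominator.

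The schedule is recommended, not mandatory. Registries are nonetheless asked to make every effort to follow it, so its order should work.

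**Conclusion.** The point holds as a conflict of ordering in the contact schedule. Given an EDD at day 280 and calendar months, the 1-month pediatric contact precedes the only fixed-date outcome contact for births before about 39w4d, and the 2-month contact does so for births before about 35w2d. For preterm births the 1-month lead is at least about 19 days and reaches about 54 days at 32 weeks, which approximate timing cannot absorb.

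The consequence is moderate: a risk of late, retrospectively collected 1- and 2-month growth, development and neurobehavioral data, concentrated in preterm infants, with some assessments missing. Contacts from 6 months on are unaffected, and deaths are not necessarily lost. The denominator effect depends on how many infants stay unassessed; at an assumed 16 live births, one or two would lower the estimate to 0.94 or 0.875 of the value among assessed infants. No figure stated in the protocol changes.

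**What to change.** Four changes, in Section 9.2.1 and Tables 4 and 5 except where noted:

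1. Extend the encouragement to report promptly to every end of pregnancy, including any live birth.
2. Time the Pregnancy Outcome Follow-Up at about 4 weeks after actual delivery when the date is known, with EDD + 4 weeks as the latest fallback when no delivery has been notified. For notified births the outcome contact then precedes the 1-month contact by 30.4 − 28 = 2.4 days at any gestational age. Carry the same timing into Section 9.3.2.4 and the abstract.
3. When a birth is learned late, retrieve the 1- and 2-month data from the pediatric record with their actual dates.
4. In Section 9.7.3.1.4, use infants assessed at each age as the denominator and report the number not assessed.

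The cost is wording. The number of contacts is unchanged. The downside is that registries must act on delivery notifications instead of one fixed calendar date.
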